7.1. Adverse Events

7.1.1. Definition of Adverse Events

An AE is defined as any untoward medical occurrence associated with the use of a drug in humans, whether or not considered drug related. An AE can therefore be any unfavorable and unintended sign, symptom, or disease temporally associated with the use of an investigational product, whether or not thought to be related to the investigational product. An AE may also constitute complications occurring as a result of protocol-mandated interventions (eg, invasive procedures such as biopsies), including the period prior to receiving the first dose of the study drug (eg, medication wash out). In addition to new events, any increase in the severity or frequency of a pre-existing condition that occurs after the participant signs the ICF is considered an AE. This includes any side effect, injury, toxicity, or sensitivity reaction.

A suspected adverse reaction is any AE for which there is a reasonable possibility that the drug caused the AE. For the purposes of expedited safety reporting, "Reasonable possibility" means there is evidence to suggest a causal relationship between the drug and the AE. Suspected adverse reaction implies a lesser degree of certainty about causality than adverse reaction, which means any AE caused by a drug.

Life-threatening AE or life-threatening suspected adverse reaction is an AE or suspected adverse reaction that, in the view of either the Investigator or the Sponsor, places the study participant at immediate risk of death. It does not include an AE or suspected adverse reaction that, had it occurred in a more severe form, might have caused death.

An AE or suspected adverse reaction is considered "unexpected" if it is not listed in the Reference Safety Information (RSI) section of the current IB or is not listed at the specificity or severity that has been observed. An SAE or serious suspected adverse reaction is an AE or suspected adverse reaction that at any dose, in the view of the either the Investigator or The Sponsor, results in any of the following outcomes:

- Death
- A life-threatening AE
- Inpatient hospitalization or prolongation of existing hospitalization
- Persistent or significant incapacity or disability (substantial disruption of the ability to conduct normal life functions)
- A congenital anomaly/birth defect
- Important medical events (IME) that may not result in death, be immediately

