7.2. Adverse Event Reporting

7.2.1. General

All AEs will be recorded from the time the study participant signs the ICF/assent until 28 days after last dose of study drug (EOS). All SAEs must be reported within 24 hours of SAE awareness on the AE eCRF via the electronic data capture (EDC) system. The Investigator is responsible for evaluating all AEs, obtaining supporting documents, and ensuring documentation of the event is complete. Details of each reported AE must include at minimum severity, relationship to study treatment, duration and outcome. All (both serious and nonserious) AEs must be followed until they are resolved or stabilized, or until reasonable attempts to determine resolution of the event are exhausted.

Any participant who experiences an AE may be discontinued from study treatment at any time at the discretion of the Investigator. The Sponsor and the CRO's Medical Monitors must be notified of the study participant discontinuation.

Note: For urgent safety issues and questions, the study Medical Monitor can be contacted 24 hours a day, 7 days a week. Contact information is located in the study binder.

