8.5. Safety and Tolerability Analyses

Safety analysis will be performed on all participants receiving at least one dose of study drug.

Adverse events will be classified according to the Medical Dictionary for Regulatory Activities (MedDRA). The incidence of TEAEs, defined as an event that occurs on or after Day 1 of study treatment or the worsening of a preexisting condition on or after Day 1 of study treatment, will be tabulated by System Organ Class (SOC), preferred term, severity, and relationship to study drug. Changes in laboratory parameters (hematology, serum chemistry, and liver function tests)

and vital signs (eg, BP, pulse, and body temperature) over time will be summarized descriptively.

SCD-related AEs will be collected and summarized separately (including VOC, ACS, osteonecrosis, priapism, etc.)

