2. INTRODUCTION

The purpose of Study GBT440-032 (C5341021) is to evaluate the effect of voxelotor on reducing the risk of stroke, as measured by transcranial doppler (TCD) flow velocity in subjects 2 to < 15 years of age with sickle cell disease (SCD) who have conditional TCD flow velocity at baseline.

This document describes the statistical methods to be used in the summary and analysis of data from Study GBT440-032. Population pharmacokinetic (PK) analyses will be described in a separate document. Descriptive statistics for **CCI** may be summarized in a separate report. Where this document differs from the study protocol, the methodology described in the SAP is considered the latest and supersedes the corresponding section(s) in the protocol.

As of 1 May 2024, study drug dosing in GBT440-032 was voluntarily paused by the Sponsor due to a safety imbalance. Study visits and other study activities continued in accordance with the protocol. Subsequently, a decision was made by the Sponsor on 25 September 2024 to terminate the study based on the totality of clinical data for Oxybryta (voxelotor) and the last subject last visit occurred subsequently.

[figure not shown]

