Completion of study is as specified on the End of Study (EOS) CRF. Subjects are considered to have completed the study if (1) the subject completed the study through the Week 96 visit and elected to enroll in the open-label extension study, or (2) the subject did not enroll in the open-label extension study and completed the study through 96 weeks plus the EOS follow-up visit (28 days after the last dose of study drug).

[figure not shown]
Change from Baseline

Change from baseline for a given endpoint is defined as the Study Visit value minus the Baseline value.

090177e1a2bf4d41\Approved\Approved On: 31-Jan-2025 17:16 (GMT)

CCI

Treatment-emergent Adverse Event

A treatment-emergent adverse event (TEAE) is defined as an adverse event (AE) with an onset date between date of first dose and 28 days after last dose, inclusive.

090177e1a2bf4d41\Approved\Approved On: 31-Jan-2025 17:16 (GMT)

Concomitant Medications

Concomitant medications are those medications taken on or after the initiation of study drug. This definition includes medications started prior to the initiation of study drug but continue concurrently with study drug.

Prior Medications

Prior medications are those medications taken prior to date of first dose.

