8.3.3. Adverse Events

AEs will be mapped to system organ class (SOC) and preferred term using the current version of Medical Dictionary for Regulatory Activities (MedDRA). AEs will be summarized according to SCD relationship.

SCD-related AEs will be summarized separately (including but not limited to sickle cell anemia with crisis, acute chest syndrome, pneumonia, priapism, dactylitis, splenic sequestration, hepatic sequestration and osteonecrosis). All other TEAEs are considered non-SCD-related TEAEs.

The total number and percentage of subjects with TEAEs will be presented by SOC and preferred term for each treatment group. TEAEs will be presented by severity. TEAEs will be tabulated presenting the SOC alphabetically, and within each system, the preferred term will be presented in decreasing order of the number of voxelotor-treated subjects who experienced each TEAE. Treatment-related AEs will be similarly presented.

The frequency of subjects who experience each TEAE or treatment-related TEAE will be determined as follows: A subject experiencing the same AE multiple times will only be counted once for the preferred term. Similarly, if a subject experiences multiple AEs within the same SOC, that subject will be counted only once for that system. If changes in the severity of an AE are recorded in the eCRF, only the most severe incidence of the AE will be counted. If a subject experiences multiple occurrences of a TEAE, only the related event or the worst severity (table dependent) will be counted for each subject within each SOC or preferred term for the summaries of treatment-related TEAEs or TEAEs by maximum severity.

Missing onset dates will be imputed as previously outlined in Section 6.4.3 as required to determine treatment-emergent events.

Listings of all AEs, TEAEs leading to discontinuation of treatment, SAEs, Grade ≥ 3 TEAEs, and deaths will be provided.

In addition, for subjects ongoing in the study at the time of the dose pause, TEAEs and SAEs that occurred during the first 28 days after the last dose of study drug will be summarized.

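### SAP Section 5 defines a TEAE by onset date alone and, without flagging it, drops the protocol's limb for worsening after Day 1, so an AE that began in screening and worsened on study drug can miss the TEAE tables

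*SAP*

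**What the plan says.** **Protocol.** Section 8.5 and the synopsis define a TEAE with two limbs: an event on or after Day 1 of study treatment, "or the worsening of a preexisting condition on or after Day 1 of study treatment".

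**SAP.** Section 5 keeps one limb, an AE "with an onset date between date of first dose and 28 days after last dose, inclusive". Section 8.3.3 also determines treatment-emergence from onset dates, imputed where incomplete. No other SAP section restores worsening for adverse events.

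**Which governs.** SAP Section 2 states that where the two documents differ, "the methodology described in the SAP is considered the latest and supersedes the corresponding section(s) in the protocol". The Summary of SAP Changes does not mention the narrower definition, and SAP Section 10 does not list it.

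**AE recording.** Protocol Section 7.2.1 starts collection at consent: "All AEs will be recorded from the time the study participant signs the ICF/assent until 28 days after last dose of study drug". Section 7.1.1 adds that "any increase in the severity or frequency of a pre-existing condition that occurs after the participant signs the ICF is considered an AE". Section 7.2.4 has a worsened preexisting condition recorded as an AE or SAE, without saying what onset date to enter.

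**Counting.** SAP Section 8.3.3 says: "If changes in the severity of an AE are recorded in the eCRF, only the most severe incidence of the AE will be counted".

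**The concern.** Worsening after first dose is an on-treatment outcome. A rule based on onset date cannot see it when the record carries a pre-dose date. Such a rule can only omit events; it cannot add any. If one arm worsens existing conditions more than the other, more events are lost from that arm and the comparison moves toward no difference.

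The by-arm TEAE tables carry unusual weight here, because SAP Section 2 reports that dosing was paused for a safety imbalance. Someone who knows the protocol definition would also expect those tables to include worsened conditions, and nothing in the SAP warns that they may not.

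**Working it through.** The plan gives no figure on this point, so the main check is a comparison of texts.

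**1. Can an AE have a pre-dose onset?** Yes. Collection starts at consent and screening lasts up to 35 days (Protocol Sections 3.1.1 and 7.2.1). SAP Section 6.4.3.2 has a date rule for AEs that occur before first dose: if only the day is missing and the month is that of treatment start, the onset is set to the day before treatment. Under SAP Section 5 such an AE is not a TEAE, whatever happens to it later.

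**2. What happens if it worsens after first dose?** There are three cases.

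| Case | Protocol 8.5 | SAP 5 |
|---|---|---|
| (a) AE begins in screening; worsening stays under the same record | TEAE, if the AE counts as a preexisting condition | Not a TEAE |
| (b) AE begins in screening; worsening is entered as a new AE dated after first dose | TEAE | TEAE |
| (c) Condition present before consent; worsens on drug and becomes an AE for that reason | TEAE | TEAE, if onset is dated at the worsening |

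The loss arises in case (a). It would also arise in case (c) if the onset were dated to the start of the condition.

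**3. Do the recording rules exclude case (a)?** Not clearly.
- Protocol Section 7.1.1 covers conditions that exist before consent and worsen afterwards.
- Section 7.2.4 covers conditions present at the start of the study, without saying whether that means consent or Day 1.
- Section 7.2.3 allows a further entry when severity changes, but for laboratory abnormalities only.
- SAP Section 8.3.3 allows for severity changes being recorded for an AE and sets no onset-date rule for them.

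**4. Where would a case (a) event still appear?** In the AE listings (SAP Sections 8.3 and 8.3.3), which give no comparison by arm. Worsening laboratory values are also covered by arm in the graded-abnormality and shift summaries (SAP Section 8.3.4).

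**5. Illustration of size.** Assume a constant AE onset rate.
- Screening: 35 days.
- First dose to end of follow-up: 96 × 7 + 28 = 700 days.
- Share of onsets before first dose: 35 / (35 + 700) = 4.8%.

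The share moves with the assumptions:
- Treatment stopped at Week 48: 48 × 7 + 28 = 364 days, and 35 / (35 + 364) = 8.8%.
- Screening of 14 days with full follow-up: 14 / (14 + 700) = 2.0%.

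Only pre-dose AEs that worsen on drug under the same record are lost. The documents give no figure for that fraction. If it were 10% to 30% (an assumption without a source), the 4.8% would become 0.5% to 1.4% of events.

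**The case against.** The strongest reply is that the visible recording rules lean toward a separate entry. The protocol treats worsening of a pre-existing condition as an AE in itself, has it recorded as an AE or SAE, and allows a laboratory abnormality to be re-entered when its severity changes. A worsening entered that way with its own onset date meets the SAP definition, and the two documents then agree. This stands. A reader might infer that every AE starting in screening and worsening on drug is certain to be missing from every TEAE table. The documents do not support that, because it depends on an eCRF convention they do not state.

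The protocol limb may also not reach the case at all. If a preexisting condition means one present at consent, an AE arising during screening falls outside it. The text leaves this open. So the proposed wording makes the limb explicit for screening AEs and is not a pure restoration.

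The counting sentence in SAP Section 8.3.3 is conditional, and could equally describe several entries reduced to one count. It shows that case (a) is possible and does not show that it is expected.

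The protocol also limits how many clinically significant AEs are open at first dose. Section 4 withdraws from screening anyone with a clinically significant change in status before randomization, and Section 6.10 requires a stable condition at screening and again before randomization. This lowers the count. Milder AEs can remain, and these have room to worsen.

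**Conclusion.** The difference between the documents is established: the SAP definition is narrower than the protocol's, the SAP governs, and the departure is not flagged. The exclusion of events is conditional. It follows when a worsening after first dose stays under a record with a pre-dose onset date, which the documents neither require nor rule out for AEs that begin between consent and first dose.

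The effect is probably small. The figure of about 5% of onsets before first dose rests on a constant rate, full-length screening and full follow-up. It should not be read as a ceiling: the dose pause shortens follow-up and raises the share, while shorter screening lowers it.

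A reader might also infer that this rule hid part of the safety imbalance behind the dose pause. The documents do not say what that imbalance was, and nothing links it to pre-dose AEs that worsened.

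The point still merits a change. A stated safety rule is narrower than the protocol's, it can only undercount on-treatment worsening, and its effect depends on an unstated recording convention.

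**What to change.** In SAP Section 5, define a TEAE as either:
- an AE with onset from first dose to 28 days after last dose; or
- an AE or condition with earlier onset whose severity increases in that window.

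Place the second kind by the date of worsening, and count it as treatment-emergent if that date is missing. Record in the SAP how this relates to Protocol Section 8.5. A further trigger for an event that becomes serious in the window would go beyond the protocol and is optional.

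The cost is one sentence and one programming condition, plus the conservative rule where the date of worsening was not collected. That rule may count some AEs that worsened before first dose. SAP Section 6.3 places the final study analysis after database lock, so the change can still apply there. Because it follows the protocol's own worsening limb, it is not a choice driven by the data.

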6. GENERAL STATISTICAL CONSIDERATIONS

6.1. Sample Size and Power

The sample size is planned to provide sufficient statistical power for the primary efficacy analysis and for a robust safety database. In addition, the number of events required to assess the secondary efficacy endpoint of time to conversion to abnormal TCD category is also considered.

For the primary endpoint (change from Baseline in TCD flow velocity [cm/sec]), assuming equal allocation across treatment groups and a common variance, an estimate of the number of subjects in each of 2 treatment groups used the following assumptions in the power calculation:

- Targeted treatment effect: difference in mean change from Baseline in TCD flow velocity is 15 cm/sec
- Common standard deviation is 24 cm/sec
- A significance level of 5% (2 -sided)

Assuming a 20% drop out rate, a sample size of 112 subjects per group provides > 95% power to detect the targeted treatment effect for the following hypothesis test using a Student's t-test:

$$H_0: \mu_1 = \mu_2 \quad \text{vs.} \quad H_A: \mu_1 \neq \mu_2,$$

where μ_1 and μ_2 stand for mean change from Baseline in TCD flow velocity at Week 24 in voxelotor and placebo groups, respectively.

For the secondary efficacy endpoint of time to conversion to abnormal TCD category, assuming 35% of subjects in the placebo group have experienced a TCD flow velocity > 200 cm/sec by Week 96, a hazard ratio of 0.5 between voxelotor group and placebo, a fixed follow up time of up to 96 weeks for each subject, and an overall 20% drop out rate, a total of 49 events is expected. This provides approximately 65% power for a log-rank test at a two-sided significance level of 5% (PASS version 11).

6.2. Randomization

Randomization will be carried out centrally through an interactive response system (IXRS). Permuted blocks within randomization strata will be used. Eligibility of the subject should be confirmed by the Investigator prior to randomization.

At the time of randomization, subjects will be stratified by HU use (yes; no), age (2 years to \leq 8 years; > 8 years to < 15 years), Screening TCD value (170 cm/sec to < 185 cm/sec;

185 cm/sec to < 200 cm/sec), and geographic region (Africa including Middle East and North Africa [MENA]; rest of world). Stratification of subjects by age was chosen to evenly balance by age distribution using the expected median age of 8 years.

6.3. Analysis Timing

The primary study analysis was performed after all randomized subjects completed the study through Week 48 or discontinued early, and all data through a corresponding data cut-off date (determined based on the last subject's Week 48 visit date) was entered in the database, reviewed, and verified. This included formal evaluation of the primary Week 24 efficacy endpoint, secondary Week 24 and Week 48 efficacy endpoints, and summary of all safety data through the data cut-off date. Summaries of Week 96 and time to event efficacy endpoints based on partial data available at this time were considered exploratory.

A final study analysis will be performed after the last subject's last visit and final study database lock. Summaries of Week 96 and time to event efficacy endpoints based on partial data will be considered exploratory due to the early termination of the study. The estimated treatment effects (voxelotor vs. placebo) and corresponding 95% CIs will be presented for these endpoints, but without formal hypothesis testing.

6.4. Handling of Data

6.4.1. Visit Windows

The conventions outlined below will be used to associate data measures, according to the study day corresponding to the date the data were collected, to an analysis visit window based on nominal (ie, planned) visits, using the measure's study day relative to Day 1. Data collected before Study Day 1 will be considered screening information with regard to assignment of visit windows. Target study days, protocol-specified ranges of study days for each scheduled visit, and the analysis visit windows defined for each nominal visit day are shown in Table 1.

090177e1a2bf4d41\Approved\Approved On: 31-Jan-2025 17:16 (GMT)

Table 1: Nominal Analysis Visit Windows

Nominal Visit Time	Target Study Day	Protocol-Specified Study Day Range	Study Day Range for Statistical Analysis
Screening	-	[-35, -1]	[-35, -1]*
Day 1	1	[1, 1]	[1, 1]
Week 2	14	[7, 21]	[2, 21]
Week 4	28	[21, 35]	[22, 42]
Week 8	56	[49, 63]	[43, 70]
Week 12	84	[77, 91]	[71, 98]
Week 16	112	[105, 119]	[99, 140]
Week 24	168	[161, 175]	[141, 182]
Week 28	196	[189, 203]	[183, 224]
Week 36	252	[245, 259]	[225, 294]
Week 48	336	[329, 343]	[295, 378]
Week 60	420	[413, 427]	[379, 462]
Week 72	504	[497, 511]	[463, 546]
Week 84	588	[581, 595]	[547, 630]
Week 96	672	[665, 679]	[631, 714]

* For TCD, all TCD data collected at Screening will be used regardless of study day.

6.4.2. Imputation of Missing Data for Evaluation of Efficacy

Guidelines regarding how missing data will be handled for each efficacy endpoint are described below.

6.4.2.1. TCD Change from Baseline

- For subjects discontinued from the study due to conversion to abnormal TCD flow velocity, missing TCD values post abnormal TCD assessment will be imputed using multiple imputation (MI). All post-baseline TCD values ≥ 200 cm/sec observed in the study for subjects with abnormal TCD will be used as the reference distribution for MI. This approach avoids the need to make a parametric assumption on the missing data given observed values, and appropriately accounts for variation due to “fill-in” missing values. See Section 8.2.1 for details.
 - A sensitivity analysis using worst observed value carried forward (WOCF) for subjects that discontinue the study early due to conversion to abnormal TCD flow velocity will also be performed (Section 8.2.8).

090177e1a2bf4d41\Approved\Approved On: 31-Jan-2025 17:16 (GMT)

- For all other subjects that discontinue the study early, missing TCD data will not be imputed.
- Subjects initiating HU postbaseline are to be discontinued from the study. TCD assessments obtained after HU initiation will be excluded from analysis.
- RBC transfusions: TCD results within 8 weeks after the transfusion date will be imputed for the MMRM analysis of TCD change from baseline. Post transfusion results will be imputed by data from the most recent study visit prior to the transfusion (including Baseline) with a non-missing TCD value.

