1. INTRODUCTION

1.1. Disease Background

Sickle cell disease (SCD) is a rare, devastating, and debilitating disease marked by the pathophysiologic features of hemolytic anemia, vaso-occlusion, and progressive end-organ damage, with a clinical course characterized by life-long disability and early death. In addition to unpredictable and recurrent episodes of severe pain, commonly referred to as painful crises, a systemic vasculopathy leads to chronic and progressive tissue injury across multiple organ systems. Multiple pathophysiologic mechanisms likely contribute to the systemic vasculopathy, including importantly, chronic hemolytic anemia (Rother, 2005).

The most devastating complication of pediatric SCD is the development of central nervous system events such as overt stroke or silent cerebral infarcts which can produce significant physical and neurocognitive deficits (Ohene-Frempong, 1998; DeBaun, 2016). Transcranial Doppler (TCD) ultrasonography to assess cerebral artery blood flow velocity in children with SCD has been shown to be a reliable predictor of stroke (Adams, 1992). Patients with "abnormal" TCD flow velocities (\geq 200 cm/sec) are at high risk of stroke, which can be mitigated by chronic red blood cell (RBC) transfusion or hydroxyurea (HU) (Adams, 1998; Adams, 2005; Ware, 2016). Because of these findings, practice guidelines recommend that all children with Sickle Cell Anemia (HbSS or HbS β^0 thal) should be screened annually with TCD according to methods employed in the STOP (Optimizing Primary Stroke Prevention in SCD) studies, beginning at age 2 and continuing until at least age 16 (NIH, 2014; Yawn, 2014).

Patients with "conditional" TCD flow velocities (\geq 170 to < 200 cm/sec) are at lower risk of stroke than patients with abnormal TCD flow velocities (risk for conditional is approximately 2% per year, for abnormal is approximately 9% per year, and for healthy children without SCD is < 0.1% per year), but still have significantly elevated stroke risk. Practice guidelines recommend that patients with conditional TCD flow velocities undergo more frequent screening and referral to specialist care for stroke prevention. Currently there is no standard-of-care therapy indicated to reduce stroke risk or prevent future need for transfusions in patients with conditional TCD flow velocities.

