5.7.2. HU Treatment

HU treatment is allowed, provided that the dose has been stable for at least 90 days prior to signing the ICF. Participants who start HU therapy for chronic use any time after randomization will be discontinued from the study.

Participants who are on HU may have their dose adjusted (based on change in their weight) if the mg/kg dose is stable.

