5.7.3. Transfusion

Participants who require chronic transfusion will be discontinued from study treatment and 28 days later undergo the EOS visit. Transfusion for surgery or trauma is permitted.

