8.2.1. Primary Endpoint

The primary analysis of change from Baseline in TCD flow velocity to Week 24 will be performed using mixed model for repeated measures (MMRM). Independent variables will include treatment, study visit, treatment by study visit interaction, and randomization stratification factors (ie, HU use, age, and Screening TCD flow velocity). Within-subject variability will be modeled using an unstructured covariance matrix. A single model will be fit incorporating available TCD flow velocity data from all timepoints, including to Week 96.

Missing data will be handled per Section 6.4.2.1. Specifically for subjects who discontinued from the study due to conversion to abnormal TCD flow velocity, missing TCD values post abnormal TCD assessment will be randomly imputed. All post-baseline TCD values ≥ 200 cm/sec observed in the study for subjects with abnormal TCD will be used as the reference distribution. Multiple imputation based on re-sampling from the reference distribution will be used. For each iteration, the imputed TCD data will be combined with the observed data, and the combined augmented dataset analyzed using the primary analysis MMRM methodology described in this section. This will be repeated 100 times and the results will be combined using Rubin's rules (Little, et al [2012] and Little and Rubin [2002]). A seed of 440032 will be used.

The primary analysis is the comparison of treatments at Week 24 for voxelotor versus placebo. The Kenward-Roger correction for denominator degrees of freedom, standard errors, and test statistics will be utilized. Sample SAS code for the MMRM will be similar to the following:

```
PROC MIXED;  
  CLASS subject treatment visit agegrp HU BTCD;  
  MODEL ChgTCD = treatment visit treatment*visit agegrp HU BTCD/ DDFM=KR;  
  REPEATED visit / SUB=subject TYPE=un;  
  LSMEANS treatment*visit / DIFF CL E OM;  
RUN;
```

Note: agegrp, HU, and BTCD are per definition of stratification factors for randomization. If there are convergence issues with the statistical model, a compound symmetry covariance matrix will be used.

The adjusted mean (lsmean) of change from baseline in TCD at each visit, with the estimated standard error and 95% confidence interval (CI), will be estimated from the MMRM model for each imputed augmented dataset. Results from the multiple imputed datasets will be combined using Rubin's rules, and results will be presented by treatment group in tabular and graphic

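### Imputation after conversion to abnormal TCD depends on why the child left, not on the observed conversion, so a converter who leaves for another stated reason is left missing at random; the likely effect is small.

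*SAP*

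**What the plan says.** SAP 6.4.2.1 gives the rule for the change-from-baseline analysis: "For subjects discontinued from the study due to conversion to abnormal TCD flow velocity, missing TCD values post abnormal TCD assessment will be imputed". The imputed values are drawn by multiple imputation from observed values of 200 cm/sec or more. For everyone else the section says: "For all other subjects that discontinue the study early, missing TCD data will not be imputed". SAP 8.2.1 repeats the trigger for the primary analysis: "Specifically for subjects who discontinued from the study due to conversion to abnormal TCD flow velocity". In SAP 8.2.8, both missing-data sensitivity analyses (worst observation carried forward and tipping point) are confined to children who leave because of conversion.

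Other rules in the same plan rest on observed values or ignore the reason for leaving:

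- **Donor pool (SAP 6.4.2.1).** Observed values of 200 cm/sec or more "for subjects with abnormal TCD will be used as the reference distribution for MI".
- **Conversion event (SAP 8.2.2.2, Table 2).** A value of 220 or more, or 200 to below 220 confirmed by a repeat of 200 or more. HU start or withdrawal censors a child only if no abnormal TCD came first.
- **Responder status (SAP 6.4.2.3).** A missing value counts as non-response for any reason.

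The protocol gives a converter other routes out. Section 5.7.2: "Participants who start HU therapy for chronic use any time after randomization will be discontinued from the study". Section 5.7.3: "Participants who require chronic transfusion will be discontinued from study treatment", followed by the end-of-study visit. Section 1.1 names these same two therapies as ways to lower stroke risk when TCD is abnormal. Section 3.4.2 adds consent withdrawal, adverse events, and investigator or sponsor discretion.

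**The concern.** Two children with the same confirmed abnormal TCD can be treated in opposite ways. One is filled in at 200 cm/sec or more. The other is left to the mixed model, which in effect predicts a return towards that arm's mean. The second child can count as a Table 2 event and donate values to the pool, yet receive none. SAP 6.4.2.1 places the conversion, HU and transfusion rules side by side without saying which takes precedence. Nothing says how attribution to conversion is determined, or that an observed qualifying value is enough.

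The first two tests in the hierarchy (change at Week 24 and at Week 48) are exposed. If converters are attributed elsewhere equally often in both arms, a true benefit shrinks slightly. If the shares differ, the estimate moves even when there is no effect: under-attribution on voxelotor favours voxelotor, and under-attribution on placebo works against it. Neither missing-data sensitivity analysis would detect this. The responder and time-to-conversion endpoints are unaffected.

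**Working it through.** **1. The plan's own figures (SAP 6.1).** 112 per arm, 20% dropout, difference 15, SD 24, 35% placebo conversion by Week 96, hazard ratio 0.5.

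- Retained per arm: 112 × 0.8 = 89.6.
- Events: 89.6 × [0.35 + (1 − 0.65^0.5)] = 89.6 × 0.5438 = 48.7. This reproduces the stated 49.
- Power with 90 per arm: 98.6% by the t distribution, which agrees with the stated figure of more than 95%.
- Standard error of the difference: 24 × √(2/89.6) = 3.59 cm/sec.

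**2. How many converters (constant hazard assumed).**

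- By Week 12: placebo 1 − 0.65^(12/96) = 5.2%; voxelotor 1 − 0.65^(12/192) = 2.7%. That is about 6 and 3 of 112.
- By Week 24: 10.2% and 5.2%, or about 11 and 6 of 112.

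A child first abnormal at Week 24 has an observed Week 24 value. With TCD every 12 weeks the Week 12 rates therefore apply, and the Week 24 rates are an upper bound. The 12-week spacing is an assumption, because the TCD rows of Protocol Appendix B are not legible in the available text.

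**3. Gap per child.** Let c be the mean imputed change (assumed 20 to 30 cm/sec, and also the child's last observed change), r the correlation between visits (assumed 0.3 to 0.7), and m the arm mean change (0 placebo, −15 voxelotor). The missing-at-random prediction is m + r(c − m), so the gap is (1 − r)(c − m).

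- Placebo: 0.3 × 20 = 6 up to 0.7 × 30 = 21.
- Voxelotor: 0.3 × 35 = 10.5 up to 0.7 × 45 = 31.5.

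**4. Shift in the Week 24 difference.** Shift = uP × pP × gapP − uV × pV × gapV, where u is the share of converters attributed elsewhere and p the conversion rate. A positive result means a smaller apparent benefit. Example at the top of the range: 0.5 × 0.0524 × 21 − 0.25 × 0.0266 × 31.5 = 0.550 − 0.209 = 0.34.

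| Share attributed elsewhere (placebo / voxelotor) | Week 12 rates | Week 24 rates (upper bound) |
|---|---|---|
| 25% / 25% | 0.01 to 0.07 | 0.02 to 0.12 |
| 50% / 50% | 0.02 to 0.13 | 0.03 to 0.25 |
| 50% / 25% | 0.09 to 0.34 | 0.17 to 0.66 |
| 25% / 50% | −0.06 to −0.14 | −0.12 to −0.29 |
| 100% / 100% | 0.04 to 0.26 | 0.06 to 0.49 |
| 100% / 0% | 0.31 to 1.10 | 0.61 to 2.14 |
| 0% / 100% | −0.28 to −0.84 | −0.55 to −1.65 |

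**5. Simulation.** One simulation used 40,000 children per arm, eight visits, TCD every 12 weeks, SD 18 to 24, effects of 8 and 15, and placebo conversion of 13% to 23% by Week 24.

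- 25% to 50% attributed elsewhere in both arms: 0.04 to 0.2 at Week 24 and 0.1 to 0.5 at Week 48.
- 50% placebo and 25% voxelotor: 0.1 to 0.35 and 0.3 to 0.75. With no true effect, about 0.3 and 0.65.
- All converters: 0.2 to 0.6 and 0.6 to 1.4.

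A second simulation at trial size (112 per arm, SD 24, 600 runs per cell) had about 23% placebo and 10% voxelotor converting at Week 12 under the 15 cm/sec effect, and about 23% in each arm under no effect. With 25% to 50% attributed elsewhere in one arm only, the difference moved by 0 to 1.0. With all converters in one arm only, it moved by 0.8 to 3.3. The placebo rate is over four times the 5.2% in step 2, so these are pessimistic. Monte Carlo error on each shift is about √2 × 3.4/√600 = 0.2, taking the runs as independent, so its smallest shifts are indistinguishable from zero.

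**The case against.** Most converters would probably be attributed correctly. Protocol 3.1.1 requires study drug to stop on a confirmed value of 200 or more, or any value of 220 or more, and Section 3.4.2.2 lists abnormal TCD as its own ground for discontinuation. HU or transfusion started because of the abnormal value can fairly be read as a consequence of conversion. This stands and limits the number exposed. It does not settle the child who withdraws consent after converting, or the missing precedence rule.

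For a transfused converter, any TCD obtained within 8 weeks is replaced by the last pre-transfusion visit value, ordinarily the abnormal one. This stands, but only for results actually obtained in that window.

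No document supports 25% to 50% attribution elsewhere, or a difference between arms. The trial is double-blind and the most revealing laboratory values are redacted to investigators. This also stands; the rates above are assumptions chosen to bound the effect.

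Reasons for leaving are tabulated by arm (SAP 8.1) and conversions are counted from TCD values, so a reader could compare the totals. That could expose a mismatch but not its effect on the estimate.

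A reader might infer that the primary result hangs on a site's choice of CRF code. The documents do not say so. The SAP takes completion status from the end-of-study form but never names the source of attribution to conversion, and an abnormal TCD assessment is required as well. A reader might also infer a bias towards voxelotor. Equal attribution elsewhere reduces a true benefit; only an excess in the voxelotor arm would favour the drug.

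**Conclusion.** The point holds as a gap in the imputation rule. The trigger adds a stated cause to an observed fact, no planned analysis tests the children this leaves out, and the plan's own event definition shows that the overlap with HU start and withdrawal can be resolved from TCD values.

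The size is small: roughly 0.04 to 0.35 cm/sec at Week 24 and up to about 0.75 at Week 48. At Week 24 that is at most about a tenth of the standard error (0.35/3.59) and about 2% of the 15 cm/sec target (0.35/15). This rests on assumed attribution rates, 12-weekly TCD, and assumed correlation and imputed values. Shifts of 1 cm/sec or more need attribution to differ strongly between arms, together with high conversion or near-total misattribution in one arm, and nothing in the documents suggests that. It should be corrected, but it is not a reason to distrust the primary result.

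**What to change.** Define imputation recipients in SAP 6.4.2.1, 8.2.1 and 8.2.8 by observed values: any child with a TCD of 220 cm/sec or more, or of 200 to below 220 confirmed by a repeat of 200 or more, followed by missing TCD, whatever reason for leaving is recorded. Then state four things:

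- Table 2's censoring for two or more consecutive missed assessments does not apply here. Pointing simply to a Table 2 event would remove imputation from converters who may now receive it.
- A value of 200 to below 220 with no repeat obtained counts as a conversion for imputation, at least in a sensitivity analysis.
- In a child who has already converted, TCD values excluded after HU start count as missing post-abnormal values and are imputed.
- The transfusion carry-forward applies only to TCD results actually obtained within its 8-week window.

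Keep the multiple imputation method, donor pool and seed. SAP 6.3 says the primary analysis was already performed, so run this as a supplementary analysis in the final analysis, labelled as added afterwards. Report by arm the number of converters not attributed to conversion; if it is zero, nothing more is needed. The cost is a flag derived from TCD data already held, a little extra analysis, and the weaker standing of a post hoc result. Sample size, alpha and stated power do not change.
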